5.2 AEs coding/grading

The verbatim term recorded on CRF will be identified as adverse event and will be coded by primary SOC and PT using Medical Dictionary for Regulatory Activities (MedDRA) version 22.1 and above.

5.3 Vital signs parameters derivations

The criteria for clinically notable abnormalities are defined as follows:

Clinically notable elevated values

- Systolic blood pressure of ≥ 140 mmHg (hypertension)
- Diastolic blood pressure of ≥ 90 mmHg (hypertension)
- Pulse rate ≥ 100 bpm (tachycardia).

Clinically notable below normal values

- Systolic blood pressure of < 90 mmHg (hypotension)
- Diastolic blood pressure of < 60 mmHg (hypotension)
- Pulse rate < 60 bpm (bradycardia)

5.4 Statistical methodology

The below SAS code will used for statistical value.

```
Frequency and proportion:
```

```
proc freq data = <.....>;
     tables response_variable/ chisq;
run;
```

Summary Statistics:

Univariate procedure will be used for continuous response.

```
proc univariate data=<.....>;
    var response_variable;
    output out=<....> n=_n mean=_mean std=_sd min=_min median=_med
    max=_max;
run;
```

95% CI

```
proc means data=adxe N NMISS CLM ;
     var aval;
run;
```

Time to event analysis

```
proc lifetest data=comb1 alpha=0.05 conftype=loglog method=KM alphaqt=0.05
outsurv=survest;
     time AVALW*cnsr(0);
run;
```

t-test

Wilcoxon rank-sum test

```
proc npar1way wilcoxon data= rnksm (label='CNV lesion area at week 12');
    class estimand;
    var area;
```

run;

AESI reported by investigator

```
if AEDECOD in ("Anterior chamber cell", "Anterior chamber inflammation",
"Vitritis", "Iritis", "Cyclitis", "Choroiditis", "Chorioretinitis", "Anterior
chamber fibrin", "Uveitis", "Noninfective chorioretinitis", "Ophthalmia
neonatorum", "Aqueous fibrin", "Uveitis-glaucoma-hyphaema syndrome", "Retinitis",
"Tubulointerstitial nephritis and uveitis syndrome", "Toxic anterior segment
syndrome", "Infective uveitis", "Vitreous haze", "Keratic precipitates", "Vitreous
abscess", "Anterior chamber flare", "Cogan''s syndrome", "Noninfective retinitis",
"Oculomucocutaneous syndrome", "Eye infection intraocular", "Iridocyclitis", "Viral
uveitis", "Viral keratouveitis", "Hypopyon", "Cyclitic membrane", "Eye
inflammation", "Optic neuritis", "Ocular pemphigoid", "Oculorespiratory syndrome",
"Idiopathic orbital inflammation", "Papillitis") then
             AEBODSYS1="Intraocular inflammation";
             AESI="Y";
else if AEDECOD in ("Choroidal infarction", "Eyeinfarction", "Macular ischaemia",
"Ocular ischaemic syndrome", "Retinal artery embolism", "Retinal artery
occlusion", "Retinal artery stenosis", "Retinal artery thrombosis", "Retinal
infarction", "Retinal ischaemia", "Retinal vascular occlusion", "Retinal vascular
thrombosis", "Retinal vein occlusion", "Retinal vein thrombosis", "Necrotising
retinitis", "Ocular vasculitis", "Retinal vasculitis", "Retinal occlusive
vasculitis") then
      do;
             AEBODSYS1="Retinal Vasculitis and / or retinal vascular occlusion";
             AESI="Y";
      end:
```

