### 12.1 Analysis sets

The Enrolled Set (ENS) includes all patients who signed an ICF and are assigned patient numbers.

The Full Analysis Set (FAS) comprises all patients to whom study treatment has been assigned and who received at least one IVT injection of study treatment.

The Safety Set includes all patients who received at least one IVT injection of study treatment.

The Per-Protocol Set (PPS) is a subset of patients of the FAS without PDs with impact. The list of PD criteria will be provided in a separate document.

However, when assessing the robustness of the overall efficacy conclusions, considerations will be given to the analysis based on the estimand using FAS and PPS. Expectation of comparing of both estimands is to have similar conclusions. Inconsistencies in the results will be examined and discussed in the Clinical Study Report (CSR).

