#### 12.4.4 Estimand and Sensitivity analyses

In case of significant outliers or deviations from normality assumptions, a non-parametric analysis may be performed.

In order to assess the robustness of the primary endpoint, estimand and sensitivity analyses are planned. These may include, but are not limited to:

- Consistent results from analyses based on the FAS and the PPS increases confidence in the trial results. Difference between FAS and PPS in incidence of intercurrent of event like COVID-19 regardless of whether patients discontinue assigned treatment. Performing comparison on the observed data between FAS vs PPS with the same handling rules for censoring as outlined in [Section 12.4.3](#). for the efficacy endpoints.
- Repeating the primary analysis using the PPS.

**Sensitivity estimand in exposed and non-exposed to the urgent safety measures:** As a sensitivity analysis for the change in CNV lesion area measured by OCT-A at Week 12, the change in CNV lesion area measured by OCT-A at Week 12 will be compared before and after the urgent safety measures were introduced. The analyses will be performed in FAS and PPS.

Further details about the analyses will be given in the SAP. Any major discrepancies in the results across analyses will be investigated as needed.

Age, Baseline lesion type, and time since nAMD diagnosis subgroup analyses will also be performed on the primary endpoint.

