2.2 Analysis sets

Enrolled Analysis Set (ENR): The ENR set includes all patients who signed an ICF and are assigned patient numbers.

Full Analysis Set (FAS): The FAS comprises all patients to whom study treatment has been assigned and who received at least one IVT injection of study treatment.

Safety Set (SAF): The SAF set includes all patients who received at least one IVT injection of study treatment.

Per-Protocol Set (PPS): The PPS is a subset of patients in the FAS without PDs with impact. The list of PD criteria will be provided in edit checks specification (ECS) document.

Full Analysis Set Estimand (FAS-EST): The FAS-EST comprises all patients who are in the FAS and did not discontinue treatment in the entire study due to COVID-19.

Per-Protocol Set Estimand (PPS-EST): The PPS-EST is a subset of patients of the FAS-EST without PDs with impact.

When assessing the robustness of the overall efficacy conclusions, considerations will be given to the analysis based on the estimand using FAS-EST and PPS-EST. The expectation for comparing both estimands is to have similar conclusions. Inconsistencies in the results will be examined and discussed in the CSR.

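### FAS-EST is defined by COVID-19 treatment stops over the whole study, so the Week 12 robustness analysis drops valid Week 12 values because of later events

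*SAP*

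**What the plan says.** **The sets.** SAP 2.2 adds two sets to the FAS and PPS. For the first: "The FAS-EST comprises all patients who are in the FAS and did not discontinue treatment in the entire study due to COVID-19". For the second: "The PPS-EST is a subset of patients of the FAS-EST without PDs with impact". Of the two analyses it says: "The expectation for comparing both estimands is to have similar conclusions". It gives no margin and no decision rule, and it sends inconsistencies to the CSR for discussion.

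**The timing.** SAP 2.5.1 sets the primary endpoint as percentage change in lesion area at Week 12, on observed data in the FAS. SAP 2.14 makes the analysis of data up to Week 12 the primary one, with a second analysis after Week 48. Protocol 12 has patients still on treatment, up to Week 40 or 44, when the first analysis is done.

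**The tables.** SAP Table 5-1 gives COVID-19 discontinuation (OTHER16) code 0 and keeps such patients in every set. Table 5-2 removes only code 1 from FAS-EST.

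**The test code.** SAP 5.4 contains "proc npar1way wilcoxon data= rnksm (label='CNV lesion area at week 12", with a class variable called `estimand` and a response called `area`. The class levels and the scale of the response are not given there.

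**The concern.** A robustness set for a Week 12 endpoint should be fixed by what has happened by Week 12. The FAS-EST wording looks forward. A patient with a usable baseline and Week 12 image, who stops for COVID-19 months later, is removed from the Week 12 comparison. Protocol 12.4.3 censors efficacy data only from the time treatment stops, so that patient's Week 12 value is valid under the protocol's own rule.

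Two consequences follow. The set selects on a later event that may be related to response or to general health. It also changes over time: at the Week 12 analysis the later stops of recently included patients are not yet known, so the same Week 12 table rerun after Week 48 could use fewer patients. In addition, a programmer working from Tables 5-1 and 5-2 and one working from SAP 2.2 would build different sets.

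The second, conditional worry is the rank-sum test. If its two classes are FAS-EST and PPS-EST, every PPS-EST patient is in both classes, and the test treats the two copies as independent. A non-significant result would then be almost automatic and could be misread as robustness.

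**Working it through.** **Inputs.** SD 35 points, 189 evaluable patients, 210 included (protocol 12.8.1 and SAP 3). The 10% difference that triggers the PPS analysis is in SAP 2.5.1. The documents give no expected share of COVID-19 stops or of PPS exclusions, so ranges are assumed.

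**The plan's own figure.** Half-width = t × 35/√n. At n = 189 this is 5.02 with Student's t, or 1.96 × 35/√189 = 4.99 with the normal value; the plan states 5.0. (1.96 × 35/5)² rounds up to 189, and 189/0.9 = 210. The plan's figures reproduce.

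**Main point: effect of late COVID-19 stops.** With a share q removed, the mean moves by q × gap, where gap is the difference between removed and kept patients. Gaps of 10 and 20 points are assumed.

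| q (assumed) | n left | half-width (t) | shift, gap 10 | shift, gap 20 |
|---|---|---|---|---|
| 1% | 187 | 5.05 | 0.1 | 0.2 |
| 5% | 180 | 5.15 | 0.5 | 1.0 |
| 10% | 170 | 5.30 | 1.0 | 2.0 |

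The 5% row removes 9 patients. SAP Table 3-1 prints 5.1 for n = 180. The numerical effect is small; the fault is that membership depends on the future.

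**Conditional point: rank-sum test on nested sets.** Let nF = 189 and nP = 189 − k, with k excluded. For a difference in means between a set and its subset:

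- SE assumed by a two-sample test: SD × √(1/nP + 1/nF)
- true SE: SD × √(1/nP − 1/nF)
- ratio: √((nF + nP)/k); for k = 19, √(359/19) = 4.35
- type I error at nominal 5%: 2Φ(−1.96 × ratio)

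| k (share) | SE ratio | type I error | 95% half-width of the true difference, SD 35, no shift |
|---|---|---|---|
| 19 (10%) | 4.35 | 1.6e-17 | 1.67 |
| 38 (20%) | 2.99 | 4.6e-9 | 2.50 |
| 57 (30%) | 2.37 | 3.3e-6 | 3.28 |
| 94 (50%) | 1.74 | 6.6e-4 | 4.96 |

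The largest type I error is 0.07%. Simulated rank-sum tests on nested sets with no difference rejected in 0.000 to 0.001 of runs.

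The extreme case is that every excluded patient lies beyond every retained one. With midranks, tie-corrected variance and continuity correction, p = 0.100 with 19 excluded, 0.058 with 22 and 0.048 with 23. So with up to 22 of 189 excluded (22/189 = 11.6%) the test cannot reach p < 0.05 whatever the excluded patients show, assuming continuous data with no ties beyond the duplicated patients.

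**The case against.** **SAP 5.4 is a set of code templates.** Table shells and programming specifications are to hold further detail. The body of the t-test code and the content of SAP 4, where the change log places an estimand analysis, do not appear in the public text. The class levels may be defined there. This stands: undefined levels in 5.4 should not be counted as a gap in the plan.

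**The nested reading is an inference.** It rests on protocol 12.1 ("considerations will be given to the analysis based on the estimand using FAS and PPS"), on the FAS versus PPS comparison in protocol 12.4.4, on SAP 2.2, and on SAP Amendment 2.0, whose superseded t-test code paired FAS-EST with PPS-EST directly above the same rank-sum block. The current heading no longer says paired. Protocol 12.4.4 also has another estimand, under which "the change in CNV lesion area measured by OCT-A at Week 12 will be compared before and after the urgent safety measures were introduced". Those groups are disjoint and a rank-sum test suits them. The code may also be only the contingency in protocol 12.4.4: "In case of significant outliers or deviations from normality assumptions, a non-parametric analysis may be performed". This stands, and it is why the second point is conditional.

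**Nobody says that p > 0.05 means robust.** A reader might infer that the SAP plans to claim similarity from a non-significant test. It does not: SAP 2.2 names no test and no p-value rule.

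**SAP 2.2 and the tables may be compatible.** SAP 2.3.2 allows exclusions for reasons other than protocol deviations, so the COVID-19 condition may be meant to apply on top of the codes. A reader might call this a flat contradiction; it is a mismatch in wording to reconcile. It leaves the whole-study time frame in SAP 2.2 untouched.

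**A similarity margin of 5.0 points would not help.** The 5.0 is a planned CI half-width, not a margin. With 19 of 189 excluded and a gap of one SD, the expected difference is 35 × 19/189 = 3.52, with SE 35 × √(1/170 − 1/189) = 0.85. The point difference falls below 5.0 with probability Φ((5.0 − 3.52)/0.85) = 0.96. This stands, and the fix uses no such criterion.

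**Conclusion.** The main point holds on the visible text alone. As worded, FAS-EST, and PPS-EST inside it, removes valid Week 12 values because of later COVID-19 stops, and neither set is final at the Week 12 analysis. Tables 5-1 and 5-2 do not match. The size depends on an unknown share: for an assumed 1% to 10% of late stops and gaps of 10 to 20 points, the mean moves by 0.1 to 2.0 points and the half-width goes from 5.02 to at most 5.30.

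The rank-sum point holds only if the classes are FAS-EST and PPS-EST. In that case type I error is at most about 0.07% for 10% to 50% excluded, and rejection is impossible with up to 22 of 189 excluded. If the classes are before and after the urgent safety measures, the overlap problem disappears. What remains is to state the scale, because the protocol asks for change there while the code label reads as raw area at Week 12.

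A reader might infer that the primary result is compromised. It is not: it is a descriptive estimate on the FAS, which neither point touches. This is a minor correction to the robustness analyses.

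**What to change.** 1. In SAP 2.2, for the Week 12 analysis, define FAS-EST (and so PPS-EST) by COVID-19 treatment discontinuation up to the Week 12 visit. Keep the whole-study condition, if wanted, for the Week 48 analysis only.
2. In SAP 5.5, state whether the SAP 2.2 condition applies in addition to the severity codes, and align OTHER16 and the FAS-EST row of Table 5-2 with the answer.
3. In SAP 5.4, name the class levels and the scale of the response.
   - If the comparison is FAS-EST with PPS-EST, drop the rank-sum test. Report each set's mean percentage change with its 95% CI, and a CI for the difference from a bootstrap that resamples patients and so respects the overlap. Report it descriptively, with no pass mark.
   - If it is the urgent-safety-measures comparison, keep the test and specify change in lesion area.

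The cost is a few sentences of SAP text and a few lines of code. No new data are needed.

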5.5 Rule of exclusion criteria of analysis sets

Table 5-1 Protocol deviations that cause patients to be excluded

Deviation ID	Description of Deviation	Exclusion in Analyses	Severity code
INCL01	Signed informed consent not obtained	Excluded from FAS and PPS analysis	1
INCL02	Age less than 50 year	Included in everything	0
INCL03	No active CNV lesions	Excluded from FAS and PPS	1
INCL04	No Intra- and/or subretinal fluid	Excluded from FAS and PPS	1
INCL05	Study eye BCVA out of range	Excluded from PPS	2
EXCL01	Active infection in either eye	Excluded from PPS	2
EXCL02	Fellow eye ocular disease	Included in everything	0
EXCL03	Poor quality images	Included in everything	0
EXCL03a	History of IOI	Included in everything	0
EXCL05	Study eye lesion area ≥50%	Included in everything	0

Deviation ID	Description of Deviation	Exclusion in Analyses	Severity code
EXCL05a	Study eye atropathy or fibrosis	Included in everything	0
EXCL07	Study eye concomitant condition	Included in everything	0
EXCL08	Study eye macula damage	Included in everything	0
EXCL09	Study eye vitreous hemorrhage	Included in everything	0
EXCL10	Study eye uncontrolled glaucoma	Included in everything	0
EXCL11	Study eye aphakaia	Included in everything	0
EXCL12	Other treatment in study eye	Excluded from PPS	2
EXCL13	Steroids in study eye	Included in everything	0
EXCL14	Prior keratoplasty/vitrectomy	Included in everything	0
EXCL15	Study eye previous ocular treatment	Included in everything	0
EXCL16	End stage renal disease requiring dialysis or renal transplant	Included in everything	0
EXCL17	Systematic drug toxic to eye	Included in everything	0
EXCL18	Participation in another study	Excluded from PPS	2
EXCL19	Systematic anti-VEGF therapy	Included in everything	0
EXCL20a	Stroke or myocardial infraction	Included in everything	0
EXCL21	Uncontrolled blood pressure	Included in everything	0
EXCL22	Malignancy	Included in everything	0
EXCL22a	Medical condition impact	Included in everything	0
EXCL24	Hypersensitivity	Included in everything	0
EXCL25	Pregnant or nursing woman	Included in everything	0
EXCL26	Women of childbearing potential	Included in everything	0
EXCL27	Minor or protected adult	Excluded from PPS	2
COMD01	Prohibited medication/procedures	Included in everything	0
COMD02	Steroids use 5 days prior to IP	Included in everything	0
TRT01	Wrong IP administered	Excluded from PPS	2
TRT02	Incorrect dose administered	Excluded from PPS	2
TRT03	Pregnancy but not discontinued	Included in everything	0
TRT04	Short treatment window between treatment	Included in everything	0
TRT05	Treatment > 3 days after injection visit	Included in everything	0
TRT06	Injection given at Week 12	Excluded from PPS	2
TRT07	Q8W IVT out of window	Included in everything	0
TRT08	Q12W IVT out of window	Included in everything	0
TRT09	COVID-19 Drug supply change	Included in everything	0

Deviation ID	Description of Deviation	Exclusion in Analyses	Severity code
TRT10	COVID-19 Treatment not given	Included in everything	0
TRT11	Missed Injection loading phase	Excluded from PPS	1
TRT12	Missed Injection	Included in everything	0
TRT13	No Disease activity but injection is given	Included in everything	0
TRT14	Treatment admin prior effic/safty evaluation	Included in everything	0
TRT15	Treatment given at EOS	Included in everything	0
WITH01	Withdrew consent not discontinued	Excluded from FAS and PPS	1
OTHER01	Patient rescreened > once	Included in everything	0
OTHER02	Severe ICH-GCP non-compliance	Excluded from FAS and PPS	1
OTHER03	New ICF is missing-rescreened	Excluded from FAS and PPS	1
OTHER04	Mishandling IP	Included in everything	0
OTHER05	Temperature excursion IP administered	Included in everything	0
OTHER06	Treatment regimen wrongly adjusted	Included in everything	0
OTHER07	Missed mandatory visit	Excluded from PPS	2
OTHER08	Missed injection visit	Included in everything	0
OTHER09	FA out of window	Included in everything	0
OTHER10	Rescreen due to BCVA results	Included in everything	0
OTHER11	Rescreen >14days w/o screening procedure	Included in everything	0
			1
OTHER13	COVID-19 Missed visit	Included in everything	0
OTHER14	COVID-19 Visit not at site	Included in everything	0
OTHER15	COVID-19 Assessment changed	Included in everything	0
OTHER16	COVID-19 Discontinuation Included in everything		0
OTHER17	Efficacy assessment not done Excluded from PPS		2
OTHER18	Safety assessment not done Included in everything		0
OTHER19	BCVA not done correctly Included in everything		0
OTHER20	Visit window > 7 days Included in everything		0
OTHER21	Vital signs/safety call not done Included in everything		0
OTHER22	Imaging analyzed after WoC Included in everything		0

Table 5-2 Patient Classification

Analysis Set	Severity codes that cause a subject to be excluded
ENR	NA
FAS	1
FAS-EST	1
PPS	1,2 (All specified PD in Table 5.1 due to COVID)
PPS-EST	1, 2 (All specified PD in Table 5.1 due to COVID-19)
SAF	NA

6 Reference

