### Study eye

4. Poor quality of OCT-A and SD-OCT images at Screening/Baseline.
5. Atrophy or fibrosis involving the center of the fovea in the study eye, as assessed by color fundus photography and fundus autofluorescence (FAF) at Screening/Baseline.
6. The total area of fibrosis or subretinal blood affecting the foveal center point comprising  $\geq 50\%$  of the lesion area in the study eye at Screening/Baseline.
7. Concomitant conditions or ocular disorders in the study eye, including retinal diseases other than nAMD, that, in the judgment of the investigator, could require medical or surgical intervention during the course of the study to prevent or treat visual loss that might result from that condition, or that limits the potential to gain visual acuity upon treatment with the investigational product.
8. Structural damage within 0.5 disc diameter of the center of the macula in the study eye, e.g. vitreomacular traction, epiretinal membrane, retinal pigment epithelium (RPE) rip/tear scar, laser burn, at the time of Screening that in the investigator's opinion could preclude visual function improvement with treatment.
9. Current vitreous hemorrhage or history of vitreous hemorrhage in the study eye within 4 weeks prior to Screening/Baseline.
10. Uncontrolled glaucoma in the study eye defined as IOP > 25 mmHg on medication or according to the investigator's judgment at Screening/Baseline.
11. Aphakia and/or absence of the posterior capsule in the study eye at Screening/Baseline.

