**Table 6-2 Prohibited medication and procedures**

Medication/Procedure	Prohibition period	Action taken
Study eye		
Any periocular injection or intraocular administration of corticosteroids (except if needed as short term treatment of AE)	Anytime	Discontinue study treatment (except if for treatment of AE)
Anti-VEGF therapy other than assigned study medication	Anytime	Discontinue study treatment
Panretinal laser, PDT laser, or focal laser photocoagulation with involvement of the macular area	Anytime	Discontinue study treatment
Any investigational drug, biologic or device	Anytime	Discontinue study treatment
Systemic		
Anti-VEGF treatment	Anytime	Discontinue study treatment
Any investigational drug, biologic or device	Anytime	Discontinue study treatment
Medications known to be toxic to the lens, retina or optic nerve, including ethambutol, chloroquine, hydroxychloroquine, deferoxamine, phenothiazines and tamoxifen (except temporary use for COVID-19 treatment)	Anytime	Discontinue study treatment

PDT: photodynamic therapy

In the fellow eye, treatment with investigational product (drug, biologic or device) is prohibited. Any marketed medication used to treat the fellow eye should be recorded in the appropriate eCRF page.

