2.5 Analysis of the primary objective

2.5.1 Primary endpoint

OCT-A will be used in this study to assess the morphological response of patients to brolucizumab. In terms of percentage change in CNV lesion area (at the biggest surface) (mm²).

The primary endpoint is the percentage change in CNV lesion area measured by OCT-A from Baseline to Week 12 in the study eye. The percentage change from Baseline at Week 12 in the lesion area will be derived as follows:

([Lesion area at Week 12 – Lesion area at Baseline]*100)/ Lesion area at Baseline

Descriptive statistics (n, mean, std, median, min and max) for the primary endpoint (actual value, change from Baseline, percentage change from Baseline) will be presented based on observed data using the FAS. Furthermore, a 2-sided 95% CI using Student's t-distribution will also be provided. In case of significant outliers or deviations from normality assumptions then IQR will be presented.

The last observation carried forward (LOCF) method will be used as sensitivity analysis to impute missing record for CNV lesion area at post baseline. If there is significant amount of missing record then another table with LOCF records should be created.

The above analysis will be done only on the study eye. The analysis will be performed on FAS. The analysis will be performed on the PPS, if there is more than a 10% difference in patients, between the FAS and PPS.

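### The per-protocol set keeps uncensored prohibited study-eye treatment up to Week 12 and graded but poor baseline OCT-A images, and its repeat of the primary analysis depends on a headcount

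*SAP*

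**What the plan says.** SAP 2.2 defines the set as follows: "The PPS is a subset of patients in the FAS without PDs with impact". Table 5-1 assigns each deviation a severity code, and Table 5-2 removes only codes 1 and 2 from the PPS and the PPS-EST. Code 0 removes nobody.

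- COMD01, "Prohibited medication/procedures": code 0. By its label it corresponds to protocol Table 6-2, whose study-eye rows include "Anti-VEGF therapy other than assigned study medication" and "Panretinal laser, PDT laser, or focal laser photocoagulation with involvement of the macular area", as well as periocular or intraocular steroid unless given short-term for an AE.
- EXCL03, "Poor quality images": code 0. The matching protocol exclusion criterion is "Poor quality of OCT-A and SD-OCT images at Screening/Baseline".
- EXCL12, "Other treatment in study eye", i.e. nAMD treatment before entry: code 2, out of the PPS.

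SAP 2.5.1 bases the primary analysis on observed FAS data and repeats it on the PPS only "if there is more than a 10% difference in patients, between the FAS and PPS". Protocol 12.4.4 lists the PPS repeat with no threshold, as one example of the robustness analyses that might be done, and says that agreement between FAS and PPS adds confidence in the results.

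**The concern.** A per-protocol analysis is useful when it removes the deviations most likely to distort the endpoint. Here the endpoint is the percentage change in OCT-A lesion area, with baseline area as the divisor. Another anti-VEGF or a macular laser in the study eye before the Week 12 image could change the numerator, and a poor baseline image could make the divisor unreliable. Both stay in the PPS, while nAMD treatment before entry does not. If such patients contribute a Week 12 value, FAS and PPS share the same distortion, and their agreement says nothing about it.

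The 10% condition adds a separate weakness. It counts patients, whereas the effect of excluding them depends also on how differently they responded. A small group with very different responses can move the mean without triggering the analysis.

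**Working it through.** **1. Can a prohibited treatment reach the primary analysis?** Protocol Table 6-2 answers study-eye anti-VEGF or laser with discontinuation of study treatment, and protocol 12.4.3 then censors efficacy data. Two gaps remain.

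- Censoring is tied to stopping or interrupting study treatment, not to the prohibited treatment itself. No study injection is scheduled between Week 8 and Week 16, so a prohibited treatment in Weeks 8 to 12 need not show up as a missed injection by Week 12.
- SAP 2.1.1 says of patients who stop treatment but stay in the study that their efficacy data are used at that time. The protocol says censored. SAP 2.5.1 does not restate the censoring.

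A concrete route: an anti-VEGF given at an unscheduled visit after Week 8 is handled as prohibited treatment under protocol 9.1.1. The early-discontinuation assessments follow 4 weeks after the last study injection and include OCT-A (Table 8-1). From Week 8 that is Day 56 + 28 = Day 84, inside the SAP's Week 12 window of Day 71 to 97. The SAP does not say whether such an assessment is mapped to Week 12. If it is, and censoring is not applied, the value enters the FAS and stays in the PPS.

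**2. Can a poor baseline image reach it?** The investigator alone assesses eligibility, and the reading center measures the area (protocol 8.3.1). An image of poor quality that is still graded yields a percentage change and stays in both sets. An image with no measurable area yields none.

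**3. The plan's precision figure.** Inputs from protocol 12.8.1: SD 35, 95% two-sided, half-width 5.0.

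- Normal quantile: (1.96 × 35 / 5)² = 188.2, rounded up to 189. This reproduces the plan.
- t quantile at n = 189: half-width 5.02. A strict limit of 5.0 needs 191.
- 189 / 0.9 = 210. This also reproduces.

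**4. What the 10% condition can leave unseen.** Let f be the share of FAS patients excluded from the PPS and D the excluded-minus-kept difference in mean percentage change. Then mean(FAS) − mean(PPS) = f × D. With 210 patients, up to 21 can be excluded without exceeding 10% (18 if counted on 189 evaluable). The documents give no D, so it is assumed, and f is taken as 10% among patients with a Week 12 value.

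| Assumed D (points) | f × D at f = 0.10 | Share of half-width 5.0 |
|---|---|---|
| 10 | 1.0 | 20% |
| 20 | 2.0 | 40% |
| 35 (one SD) | 3.5 | 70% |

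**5. What the retained COMD01 and EXCL03 patients could do.** With k such patients among 189, the mean moves by k/189 × D. The values of k are also assumed.

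| k | D = 20 | D = 35 |
|---|---|---|
| 2 | 0.21 | 0.37 |
| 5 | 0.53 | 0.93 |
| 10 | 1.06 | 1.85 |

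**6. Precision cost of recoding.** The t half-width goes from 5.02 at 189 to 5.05, 5.09 or 5.16 after dropping 2, 5 or 10 patients.

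**The case against.** The strongest reply is that the plan already handles most of this.

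- The primary estimand is the effect while on study treatment, and protocol 12.4.3 censors once treatment stops. After the early-discontinuation assessments, no further OCT-A is scheduled. This stands for patients who were stopped and censored as the protocol describes. It does not cover those who were not stopped, or the SAP's differing wording.
- EXCL12 and COMD01 differ for a reason: previous treatment breaks the treatment-naive population and cannot be censored, while on-study use can. COMD01 also covers systemic drugs and use after Week 12, which cannot affect the Week 12 image. This stands, and it argues for splitting COMD01 rather than recoding all of it.
- Unmeasurable baselines drop out, and the sample size allows for uninterpretable images. This stands; only graded but poor images are at issue.
- The PPS repeat is only one of the protocol's possible analyses, so the SAP's condition is not a clear contradiction. The comparison of FAS-EST with PPS-EST, and the protocol's before/after urgent-safety-measure analysis in FAS and PPS, carry no stated headcount condition. This stands, but PPS-EST uses the same codes and has the same blind spot.

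A reader might infer that the PPS cannot check the primary result at all. The documents do not support that. The PPS removes wrong product or dose, an injection at Week 12, missed mandatory visits, efficacy assessments not done and previous nAMD treatment. It also removes missed loading injections (TRT11), although TRT11's code 1 would take those patients out of the FAS too, contrary to its own description. Nor do the documents show that both sets will credit brolucizumab with another drug's effect; that requires the uncensored route in step 1 of the working.

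**Conclusion.** The point holds in a limited form. As coded, the PPS and PPS-EST cannot show the effect on the primary endpoint of uncensored prohibited study-eye treatment up to the Week 12 OCT-A, or of poor but graded baseline OCT-A images. That fits badly with a set defined as free of deviations with impact. The SAP may also not repeat the primary analysis on the PPS at all, on a criterion unrelated to whether results differ.

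The size is unknown. The documents give neither the frequency of these deviations nor the difference in response. The 35-point difference is the planning SD used as an illustration, and the 3.5-point figure belongs to the 10% condition, not to COMD01 or EXCL03. For those two rows, 2 to 10 patients of 189 move the mean by about 0.2 to 1.9 points under the assumed differences, inside the planned half-width. The analysis is single-arm and descriptive, and the PPS is supportive, so this is a cheap improvement rather than a threat to the trial. SAP Section 4, on changes to protocol-specified analyses, has no text in the copy available, so a relevant rule there cannot be ruled out.

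**What to change.** 1. Split COMD01 in Table 5-1. Give code 2 to prohibited anti-VEGF, PDT or macular laser, and intraocular or periocular steroid other than for an AE, in the study eye on or before the Week 12 OCT-A. Leave all other COMD01 events at 0.
2. Give EXCL03 code 2 where the baseline OCT-A is of poor quality.
3. Delete the 10% condition in SAP 2.5.1 so that the PPS analysis is always reported.
4. Reconcile the treatment-discontinuation definition in SAP 2.1.1 with the censoring rule in protocol 12.4.3, and restate the agreed rule in SAP 2.5.1.

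The cost is a few table and text edits and a slightly smaller PPS: a half-width of about 5.16 instead of 5.02 if 10 of 189 patients are dropped. Excluding patients for a post-baseline event also brings some selection, because a prohibited treatment may follow a poor response. That is usual for a supportive per-protocol analysis and should be acknowledged when the result is reported.
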